We will use online, electronic surveys (i.e., RedCap) for all employees, supervisors, and spouses/partners at baseline and at 4-months and about 9-months post-baseline, following supervisor FSSB/Sleep Leadership training and in-person sleep/cognitive effectiveness feedback for the treatment group. We will also conduct a COVID-related survey in November 2020 to assess the effects of the pandemic. Surveys will be completed OFF of work time. In addition, we will collect objective sleep data with actigraphy devices at baseline and 9-month post-baseline as an objective health indicator from employees and their supervisors. We will be using the same actigraphy devices, and all participants will be wearing the watches for 3 weeks at baseline and 9-month post-baseline. Supervisors in the treatment condition will also be briefly surveyed at the time of training using a survey program within the computer-based training module. All supervisors – regardless of study conditions – will be invited to participate in the baseline & follow-up surveys assessing their knowledge of FSSB and sleep leadership concepts & assessing outcomes related to our hypotheses. All spouses/partners who live with the employees will also be invited to participate in the survey study at baseline, 4- and 9-month post-baseline. Spouse/partners will not participate in any of the actigraphy data collection.

Upon completion of data collection, we will use the actigraph data collected from baseline and 9-month post-baseline to generate feedback reports (e.g., comparison estimates) for all participants in both intervention and control groups. These reports will only be used for feedback purposes, they are not part of the intervention. The actigraph data collected from baseline and 9-month post-baseline will also be used for our internal data analyses (e.g., combined with survey responses for statistical analyses and hypothesis testing). Note that the current study is simply using the actigraphy devices to collect data related to participants' sleep and their daily activities. We are not testing the efficacy of the devices.

(7) Data and Specimens

Handling of Data and Specimens

Confidentiality of participants' responses will be maintained. Results will only be reported in aggregate form. Data from the online surveys and actigraphic assessments will be kept on our secure server at OHSU and only designated persons from our research team will have access. The REDCap program monitored by the Oregon Clinical & Translational Research Institute (OCTRI) at OHSU will be used for all survey data collection. It is designed to handle data collected from human subjects, while systematically accounting for related confidentiality issues.

It is also HIPAA compliant. Further, the data are protected behind a firewall and is accessible only by authorized research staff with a login and password combination, thus ensuring the confidentiality of all survey responses, email addresses, and personal information.

Steps to be taken to protect the safety and confidentiality of all participants include the use of study code numbers for identification, data linkage of employee surveys, spouse/partner, and supervisor data. Participant unique identification numbers will be used to match survey responses between employees, their supervisors, and their spouses/partners. After merging the responses, the final datasets used for data analysis will be completely de-identified. Additional steps taken will include, reporting of aggregate data, and destroying all identifiers within three years after completion of the study. Participant code number lists and participant contact information will be kept in separate locked file cabinets. We plan to store the de-identified data (data from the online surveys and actigraphic assessments) indefinitely after the end of the study on our secure server at OHSU and on Box; only designated persons from our research team will have access.

Researchers collecting data for the proposed study will follow all guidelines and protocols as authorized by the OHSU Research Integrity Department/Institutional Review Board. Personally identifying information such as name and phone number will be used strictly for recruitment, and scheduling. All contact information will be securely stored in a separate locked file cabinet in a locked office by research staff and will be destroyed within three years of study completion.

Sharing of Results with Subjects

Individual-level sleep/cognitive effectiveness feedback will be distributed in person to those in the intervention group as part of the intervention design. Individualized reports containing actigraphic measurements and summary estimates relevant to participants' own sleep habits, sleep quality, sleep quantity, etc. will be shared with participants during the sleep/cognitive effectiveness feedback intervention period (around 1-month post baseline; during intervention phase). Aggregated results without any identifying information will also be shared via email to all participants. Their email addresses and other identifying information will be kept separate from the individual-level data.

Upon completion of data collection, we will use the actigraph data collected from baseline and 9-month post-baseline to generate feedback reports (e.g., comparison estimates) for all participants in both intervention and control groups. These reports will only be used for feedback purposes, they are not part of the intervention.

(8) Data Analysis

Descriptive and Psychometric Analyses:

As we are exclusively using established and validated measurement instruments, we do not anticipate psychometric problems. However, we will perform the standard set of psychometric analyses on each of these measurement instruments to verify their performance with the current sample. Analyses will include descriptive item and scale statistics and verification of scale reliabilities and factor structures. Assessment of scale reliabilities (e.g., Cronbach's alpha) and factor structures will use established confirmatory factor analysis methods. In the event that we find poorly performing measurement instruments, we will explore whether better psychometric performance can be obtained by deleting some of the scale items, as long as doing so is theoretically defensible.

Power Analysis:

This section documents the power analyses we conducted for the planned analyses for hypothesis testing. We focus on power for the analyses involving employee-level outcomes. To estimate power for Service member-level outcomes, we based our effect size estimate for the intervention's effect on physical health from the data reported in Hammer et al. (2011), i.e., $d = .33$ ($ICC = .03$) after controlling for baseline physical health and a workplace intervention's effect on sleep problems ($d = .30$; $ICC = .01$) from (Adler, Gunia, Bliese, Kim & LoPresti, working paper). We assumed 24 randomized clusters. Throughout, we set alpha = .05 to define statistical significance. Power analyses for the employee-level outcomes were conducted using Optimal Design (Version 2.01) software package (Raudenbush, Spybrook, Congdon, Liu, and Martinez, 2011). With these assumptions, the estimated power for the effect of the intervention on physical health would be .95 and on sleep problems would be .83 with 500 enrolled employees at baseline. Assuming an attrition rate of 20% (see Missing Data discussion below) resulting in a total sample size of 400 employees across the 24 randomized clusters, the estimated power for the effect of the intervention on physical health would be .86 and on sleep quality would be .80. Thus, we have demonstrated adequate power to test our hypotheses for employees.

Missing Data and the Application of Intent-to-Treat:

Missing data intermittently during the study and/or dropouts are inevitable and an issue faced by all longitudinal studies. There is no consensus, however, on the optimal analytical strategy to analyze missing data. Using the standard missing data taxonomy (Rubin, 1987), we will follow the recommendations made by Nich and Carroll (1997, 2002) and conduct intent-to-treat analyses using three strategies. In the first strategy we will extend the multiple imputation method of Little and Yau (1996) to allow for non-monotone missing values, which could occur intermittently during the study period. Monotone missing patterns require subsequent variables to be missing once a variable is missing. We will impute unobserved outcomes based on study condition, observed subject-level covariates at baseline and observed follow-ups. Inferences will be made on imputed datasets using Rubin's method (Barnes, Lindborg, & Seaman, 2006; Rubin, 1996). Our second analytical strategy will consider selection models and pattern-mixture models (Michiels, Molenberghs, Bijnens, Vangeneugden, & Thijs, 2002) based on different factorization of the joint distribution of the response variables and the missing patterns. As different strategies require different assumptions for the estimated treatment effects to be unbiased and some assumptions are not testable, comparisons of these strategies serve mainly as sensitivity analyses of their influence on the estimated key parameters of each Aim. A third strategy will consider the use of Full Information Maximum Likelihood methods in the analysis of incomplete data as implemented in several software programs (e.g., Mplus; Muthén & Muthén, 2007). As mentioned in the prior section, this study is adequately powered for an attrition rate of 20%.

Analysis of Research Questions/Hypotheses:

The data for this study are generated from a cluster randomized experimental design with all participating supervisors and their employees within a facility cluster randomly assigned to either an intervention or usual practice control condition. Standard general linear and generalized linear mixed model approaches for cluster randomized designs (i.e., hierarchical linear models, multilevel models; Murray, 1998; Murray, Varnell, and Blitstein, 2004) will be used for data analysis for our research questions/hypotheses to account for the nesting structure in the data. As these models are now widely used and understood and are available in numerous statistical software packages, our discussion here on the specifics of these analyses will be brief. In each case, link functions for these models will be determined by the scaling of each outcome variable. Furthermore, in each analysis we will use the outcome variable at baseline as a predictor in the model to adjust for unexpected imbalance from randomization and

to increase the statistical power for and precision of parameter estimates. Cluster differences will be modeled as random effects. Finally, the recruitment wave (i.e., block), rank, gender, unit type, marital status, and mental health symptoms will be used as predictors in the statistical models. Of interest in these models is the direction, magnitude, and statistical significance of the parameter corresponding to the indicator of intervention group, which appears at the organization level of the multilevel analysis. For example, Physical Health scores at 4-months will be regressed on an indicator of intervention condition and Physical Health scores at the pre-intervention assessment, minimally specifying a random effect for the intercepts across organizations. As needed, depending on attrition and missing data, this basic generalized linear mixed model will be extended in the analysis of the specific aims as mentioned in a prior section (e.g., multiple imputation for missing predictor variable values, FIML estimation for missing outcome variable values).

(9) Privacy, Confidentiality and Data Security

Confidentiality of participants' responses will be maintained. Results will only be reported/published in aggregate form. Data from the online surveys and actigraphic assessments will be kept on our secure server at OHSU and on Box; only designated persons from our research team will have access. REDCap is designed to handle data collected from human subjects, while systematically accounting for related confidentiality issues. The data are protected behind a firewall and is accessible only by authorized research staff with a login and password combination. REDCap also meets the privacy standards set forth by the Health Insurance Portability and Accountability Act (HIPAA), ensuring the confidentiality of all survey responses, email addresses, and personal information.

Steps to be taken to protect the safety and confidentiality of all participants include the use of study code numbers for identification, data linkage of employee surveys, spouse/partner, and supervisor data. Only OHSU personnel in this project, specifically [name], [name] and [name], will have access to the code key. Additional steps taken will include, reporting of aggregate data, and destroying all identifiers within three years after completion of the study. Participant code number lists and participant contact information will be kept in separate locked file cabinets.

Researchers collecting data for the proposed study will follow all guidelines and protocols as authorized by the OHSU Research Integrity Department/Institutional Review Board. Personally identifying information such as name and phone number will be used strictly for recruitment, and scheduling. All contact information will be securely stored in a separate locked file cabinet in a locked office by research staff and will be destroyed within three years of study completion.

(10) Risks and Benefits

Risks to Subjects

Efforts will be made to minimize risks associated with this study. Minimal potential risks for participation include breaches of confidentiality associated with data collected for research purposes and minimal psychological distress associated with the psychological distress survey measures and sleep feedback. Additional potential, but not expected, risk is that a supervisor may be upset about being contacted to participate in a study or may not like the supervisor training. Supervisors can discuss these issues at any time with research staff.

Risk management and emergency response:

To mitigate potential distress related to the psychological well-being survey items, participants will be made aware that participation is completely voluntary and that they are welcome to withdraw involvement at any moment without consequence. The data is protected behind a

firewall and is accessible only by authorized research staff with a login and password combination. Further, surveys are securely protected under the REDCap survey program, which meets the privacy standards set forth by the Health Insurance Portability and Accountability Act (HIPAA), ensuring the confidentiality of all survey responses, email addresses, and personal information. Additionally, a list of resources to assist with psychological and physical distress, family resources, at both the state and national level will be provided on our study website.

Potential Benefits to Subjects

We expect positive results for all study participants, including reduced stress and increased social support. Employees of these supervisors are also expected to benefit from this training because the supervisors are expected to be more supportive of their employees. Longer term, these effects are expected to create a more supportive work environment for study participants, which has positive effects on safety, health, well-being, family, and organizational outcomes among participating employees, supervisors, and spouses/partners. We also expect that providing study participants (from both intervention & control groups) with individual/personalized sleep feedback will reduce sleep problems and improve sleep awareness.

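### Three of the four stated power figures do not follow from the stated inputs; on a two-sided test they are lower, and both outcomes fall below .80 after 20% attrition

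*Combined protocol and SAP*

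**What the plan says.** The Power Analysis in section (8) of the combined protocol and SAP lists d = .33 with ICC .03 for physical health, d = .30 with ICC .01 for sleep problems, 24 randomised clusters and alpha .05, and names Optimal Design as the software. The physical-health effect is described as obtained "after controlling for baseline physical health". From these inputs it reports that, with 500 employees, "estimated power for the effect of the intervention on physical health would be .95 and on sleep problems would be .83". It then assumes 20% attrition, "resulting in a total sample size of 400 employees across the 24 randomized clusters", and reports that "the estimated power for the effect of the intervention on physical health would be .86 and on sleep quality would be .80".

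Two conclusions rest on these numbers. The Power Analysis closes with "Thus, we have demonstrated adequate power to test our hypotheses for employees", and the Missing Data section repeats that "this study is adequately powered for an attrition rate of 20" percent.

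The analysis section later in (8) adjusts every outcome for its baseline value, in part "to increase the statistical power for and precision of parameter estimates", and adds that "the recruitment wave (i.e., block), rank, gender, unit type, marital status, and mental health symptoms will be used as predictors". The power text does not state whether the test is one- or two-sided, what R-squared (if any) was entered at either level, or whether blocking was included.

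**The concern.** The plan presents the four figures as the direct result of the listed inputs, so a reader should be able to recover them. Their pattern looks wrong before any calculation. Physical health has a slightly larger effect than sleep (.33 against .30) but three times the ICC. With about 20 people per cluster the ICC dominates, so physical health should have the lower power. The plan gives it the higher power at both sample sizes. The fall from .95 to .86 is also steep for a 20% loss of people with no loss of clusters.

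These are the only power figures in the plan. If they are overstated, a null result could be read as stronger evidence against an effect than the design supports. For physical health after attrition, the printed .86 implies a type II error of 14%; on the stated inputs it is about 26%.

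**Working it through.** **Inputs.** From the Power Analysis: J = 24 clusters, alpha = .05, N = 500 or 400, and the d and ICC values above. From section (6), Procedures Involved: half the clusters go to each arm. Assumed because not stated: two-sided test, equal clusters, no further R-squared. Sleep quality at N = 400 is taken to be the same outcome as sleep problems at N = 500, since no other inputs are given for it.

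**Formula.** With n = N/24 per cluster, Var = 4 × [ICC + (1 − ICC)/n] / J. The noncentrality is λ = d/√Var, and power comes from the noncentral t with J − 2 = 22 df.

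- Physical health, N = 500 (n = 20.83): Var = 4 × (.03 + .97/20.83)/24 = .01276; λ = .33/.1130 = 2.92; power .797.
- Physical health, N = 400 (n = 16.67): Var = .01470; λ = .33/.1212 = 2.72; power .739.
- Sleep, N = 500: Var = 4 × (.01 + .99/20.83)/24 = .00959; λ = .30/.0979 = 3.06; power .833.
- Sleep, N = 400: Var = .01157; λ = .30/.1075 = 2.79; power .760.

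A simulation of 60,000 runs gives .798, .739, .833 and .758. Sleep at N = 500 matches the plan, which suggests that this is the intended type of calculation.

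**Other settings tried.**

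| Setting | Physical health 500 / 400 | Sleep 500 / 400 |
|---|---|---|
| Stated in the plan | .95 / .86 | .83 / .80 |
| Two-sided t, 22 df | .80 / .74 | .83 / .76 |
| Planned block sizes, 22 df | .80 / .74 | .83 / .76 |
| Planned block sizes, 20 df | .79 / .73 | .83 / .76 |
| One-sided t | .88 / .84 | .91 / .85 |
| Two-sided normal | .83 / .78 | .87 / .80 |
| One-sided normal | .90 / .86 | .92 / .87 |
| Cluster-level R-squared .87, two-sided t | .93 / .87 | .89 / .81 |
| R-squared .15 at both levels, two-sided t | .86 / .81 | .89 / .82 |

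The planned block sizes come from the Randomization Design Plan: 75, 100 and 75 employees per arm, each over 4 clusters, so 18.75, 25 and 18.75 per cluster. The 20-df row removes 2 df for block. The R-squared values are illustrations, not limits. No row gives all four printed figures.

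**Checks that do not depend on sidedness or on t versus normal.**

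1. *Ordering.* λ is lower for physical health than for sleep at both sizes (2.92 against 3.06; 2.72 against 2.79). With no further R-squared, power for physical health must therefore be lower. The plan prints it higher.
2. *The pair .95 and .86.* With all 24 clusters kept, losing 20% of people multiplies λ by at least √.8, the limit when the ICC is zero. Power of .95 on the two-sided t needs λ = 3.77; 3.77 × √.8 = 3.38, which gives .897. Starting from .945 to allow for rounding gives .889, and also rounding cluster sizes from 21 to 16 gives .874. None reaches .86. The one-sided t gives higher floors and the normal approximation nearly identical ones.
3. *The .95 itself.* At the stated ICC, the highest value among the four one- and two-sided t and normal calculations is .90. On a two-sided t, even an ICC of zero gives only .941.

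**Effect size implied by the printed values.** On the two-sided basis, physical health would need d of about .43 for .95 at N = 500 and about .39 for .86 at N = 400, against the stated .33. The two values also differ from each other.

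**The case against.** The strongest reply is that zero R-squared is the reviewer's choice and not the plan's. The analysis section commits to baseline adjustment and several further predictors, so some gain is expected even though its size is not given. It need not be large: with R-squared of about .14 (physical health) or .095 (sleep) at both levels, power at N = 400 returns to .80. The phrase about baseline adjustment is attached only to physical health, so a baseline gain for sleep is not excluded. Moreover, one unstated setting (cluster-level R-squared .87 with 16 people per cluster) gives .860 and .798, which print as the two post-attrition figures. Sidedness is unstated, and the 4-point miss for sleep depends on treating the two sleep labels as one outcome. Finally, enrolment was probably over before the last approval, and a corrected power figure changes no estimate or test.

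Much of this stands, and it limits the conclusion: the trial is not shown to be underpowered. It does not rescue the printed figures. The .87 setting, with 21 people per cluster, gives .93 and .89 at N = 500 against .95 and .83. No setting tried reproduces all four values, and the ordering and attrition checks do not turn on sidedness. For physical health, a further baseline gain is doubtful because d is already described as adjusted. That the correction is only to text makes it cheap; it does not make the stated figures right.

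**Conclusion.** The concern holds. On the stated inputs with a two-sided test, 22 df, 24 equal clusters and no further R-squared, power at N = 500 and 400 is .80 and .74 for physical health (stated .95 and .86) and .83 and .76 for sleep (stated .83 and .80). Three of the four figures are overstated, by about 15, 12 and 4 points. The physical-health contradiction is the firmest; the sleep miss at N = 400 assumes that one sleep outcome is meant.

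On this basis both outcomes fall below .80 after 20% attrition. For both to reach .80, a setting the plan does not give is needed, such as a one-sided test or a covariate R-squared of a stated size; a plain two-sided normal approximation lifts sleep to .80 but leaves physical health at .78. Adequate power is therefore not demonstrated by the plan as written.

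**What to change.** Rerun all four figures under one disclosed setting and replace the printed values. State sidedness, cluster size, degrees of freedom, R-squared at each level, and whether d = .33 already contains the baseline adjustment. Use one name for the sleep outcome.

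If no further setting was used, restate power as .80 and .74 (physical health) and .83 and .76 (sleep) at N = 500 and 400, labelled as two-sided, 24 equal clusters, no further covariate R-squared. If a covariate gain was entered, give its value and source.

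Make the adequacy sentences in the Power Analysis and Missing Data sections conditional on that setting. The cost is a text change, with the possibility that the stated power becomes less favourable. Enrolment, model and tests are unaffected.

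### The outcome imputation model leaves out the randomised cluster, so the pooled standard error of the treatment effect is up to about 6% too small at the plan's ICC of .03

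*Combined protocol and SAP*

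**What the plan says.** All references are to the combined protocol and SAP.

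- **Section (8), Missing Data and the Application of Intent-to-Treat.** Three intent-to-treat strategies are listed. The first is multiple imputation of outcomes: "We will impute unobserved outcomes based on study condition, observed subject-level covariates at baseline and observed follow-ups". The only extension of the cited imputation method that is mentioned is to non-monotone missingness. Pooling is by Rubin's rules ("Inferences will be made on imputed datasets using" that method). Selection and pattern-mixture models come second and FIML third. The section says that "comparisons of these strategies serve mainly as sensitivity analyses", but it does not say which strategy is the main one.
- **Section (8), Analysis of Research Questions/Hypotheses.** The analysis is a mixed model: "Cluster differences will be modeled as random effects". As an example of how it may be extended when data are missing, the section gives imputation for predictors and "FIML estimation for missing outcome variable values".
- **Section (8), Power Analysis.** "We assumed 24 randomized clusters". It uses 500 employees, 20% attrition leaving 400, ICC .03 for physical health and ICC .01 for sleep problems.
- **Section (6), Procedures Involved.** Surveys are at baseline, 4 and 9 months. For actigraphy, "we will collect objective sleep data with actigraphy devices at baseline and 9-month post-baseline" only.

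**The concern.** In a cluster-randomised trial the between-cluster variance largely sets the precision of the treatment effect. An imputation model without cluster draws each missing outcome around the arm's regression line, independently of who else is in the cluster. The completed data then hold less between-cluster variation than the real data, and the mixed model fitted to them reports an SE that is too small. Rubin's between-imputation term reflects uncertainty under the imputation model as specified, so it does not put the lost cluster variance back.

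Another observed follow-up of the same outcome carries part of the cluster effect and reduces the problem. Actigraphic sleep has no second follow-up of the same measure, and a participant who leaves before month 4 has none for any outcome.

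At stake are the width of the intervals from this strategy and the meaning of the comparison between strategies. If the imputation interval is narrow because cluster was left out, a difference from FIML could be misread as an effect of the missing data. Because no primary method is named, the imputation result could also be reported as the main one.

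**Working it through.** **Inputs.** From Power Analysis: J = 24 clusters, N = 500 (m = 500/24 = 20.83 per cluster), missing fraction f = .20, ICC ρ = .03 or .01. From Procedures Involved: half the clusters to each arm. Assumed: equal cluster sizes, data missing completely at random, unit variance, two-sided α = .05.

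**The plan's own figures.** The plan gives no SE for the imputation analysis. As a check on the complete-data variance formula, SE = √{4[ρ + (1−ρ)/m]/J} with a noncentral t on 22 df gives power .83 for sleep at N = 500, as stated. Sleep at N = 400 gives .76 against .80. Physical health gives .80 and .74 against the stated .95 and .86. That last mismatch is a separate matter, and nothing below depends on it.

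**Correct variance** when no other follow-up is observed:

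V = 4[1 + ((1−f)m − 1)ρ] / [(1−f)N]

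At ρ = .03: 4[1 + (16.67 − 1)(.03)]/400 = 4(1.47)/400 = .0147, SE = .1212.

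**Pooled variance with cluster left out.** Only pairs in which both outcomes are observed keep the within-cluster correlation. Their share is (1−f)² = .64.

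- Within: W = 4[1 + (m−1)(1−f)²ρ]/N = 4[1 + (19.83)(.64)(.03)]/500 = 4(1.381)/500 = .01105
- Between: B = 4[f²/((1−f)N) + f/N] = 4[.0001 + .0004] = .0020
- Total = .01305, SE = .1142

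Ratio .1142/.1212 = .942, so the SE is **5.8% too small**. At ρ = .01 the SEs are .1050 and .1075, **2.4% too small**.

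A second version uses clusters of 21 and 20 imputations. The correct variance is (4/24)(.03 + .97/16.8) = .0146. The pooled variance is (4/24)(.64×.03 + .0465) + 1.05×.00198 = .0130, where .0465 = (16.8×.97 + 4.2×1)/21². The ratio is .944 (5.6%), and the shortfall is 2.0% at ICC .01. With 48 clusters it is again 5.6%, so the number of clusters does not drive the shortfall; it matters for the df.

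**Simulation under the null** (24 clusters of 21, 20% missing, 20 imputations, Rubin pooling):

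| Setting | Analysis | Pooled SE / true SD |
|---|---|---|
| ICC .03, no other follow-up (20,000 runs) | REML mixed model | .1147/.1206 = .951 |
| Same | Cluster means | .1136/.1206 = .942 |
| ICC .03, other follow-up for all, residual correlation .55 (40,000 runs) | Cluster means | .961 (mean SE), .969 (root mean square) |
| ICC .01, no other follow-up | REML / cluster means | .995 / .968 |
| ICC .03, cluster random intercept in the imputation model (10,000 runs) | REML / cluster means | 1.008 / 1.002 |
| ICC .03, no imputation, observed data | REML mixed model | 1.00 |

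Smaller separate simulations at ICC .03 with no other follow-up gave shortfalls of 5.2% (4.4% with the cluster variance truncated at zero), 5.7 to 6.4%, and 6.5% under REML (1,200 runs, Monte Carlo error about 2%). With another follow-up for everyone, the closed form gives 2.3 to 2.9% (assumed residual correlation .5 to .6). A separate simulation at correlation .6 gave 3.0 to 3.4%, and the 1,200-run REML simulation gave 0.9%.

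**Type I error** (complete-data df 24 − 2 = 22):

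| Setting | Barnard-Rubin df | Large-sample df |
|---|---|---|
| ICC .03, cluster left out | .049–.052 | .067–.071 |
| ICC .01, cluster left out | .038–.046 | .054–.062 |
| ICC .03, cluster random intercept included | .038–.040 | .054–.057 |
| ICC .03, observed-data mixed model | .046 (t, 22 df) | .058 (z) |

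A separate 6,000-run check of the first row gave .056 and .072.

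**The case against.** The case for treating this as minor is a fair one.

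- **Size.** Under the mixed model the plan specifies, the 20,000-run REML shortfall is 4.9% at ICC .03 and 0.5% at ICC .01. The figure nearest 6% comes from the closed form and from cluster means.
- **Pairing of conditions.** ICC .03 belongs to physical health, which is surveyed at both 4 and 9 months, so a second follow-up will often be available and the shortfall is then about 3%. Actigraphic sleep lacks one, but the plan's only sleep ICC is .01.
- **Type I error.** With Barnard-Rubin df it is about nominal despite the omission, and adding cluster makes the test slightly conservative. With large-sample df the omission adds only about .01; the rest of the excess is a df problem that exists anyway.
- **Other routes.** FIML within the mixed model keeps the cluster effect and is the plan's own example for missing outcomes.
- **Wording.** Cluster is missing from a one-sentence list, not expressly excluded. Unit type and block might absorb some cluster variation if they were also used in the imputation; this was not examined.

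The points on size and type I error stand as limits, which is why the figure is given as up to about 6% and only for stated inputs. They do not remove the error. The plan says what the imputation conditions on, and following it gives SEs that are too small wherever cluster variance is present. The FIML mention is an example to be applied as needed, while outcome imputation heads the list of intent-to-treat strategies. Near-nominal type I error with Barnard-Rubin df depends on a choice the plan does not make.

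**Conclusion.** The concern holds. With the plan's 24 clusters, 500 employees, 20% attrition and ICC .03, the imputation strategy as written understates the SE of the treatment effect by about 5 to 6% when no other follow-up of the outcome is observed, about 3% when one is observed for everyone, and 0 to 3% at ICC .01. Actual missingness will probably fall between the first two cases. Type I error is about .05 with small-sample df and about .07 with large-sample df at ICC .03.

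The result rests on equal clusters, data missing completely at random and the assumed correlation between follow-ups. About 6% is the ceiling for these inputs only: the same closed form gives 7.4% if the 200 supervisors are analysed with the employees (N = 700), and 8.1% if 36% of employee outcomes were missing, which is an assumption and not a figure in the plan. The mixed model fitted to observed outcomes is not affected. The error is modest, confined to one of three strategies, and should be corrected because the correction costs almost nothing.

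**What to change.** Change the text of section (8) as follows.

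1. Add a random intercept for the randomised cluster, and block, to the outcome imputation model.
2. State that imputed results are pooled with Barnard-Rubin df, with complete-data df based on the number of clusters.
3. Name the mixed model on all observed outcomes as the primary analysis, fitted by REML with between-cluster or Kenward-Roger df.
4. Label multiple imputation and the selection and pattern-mixture models as sensitivity analyses.

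The cost is SAP wording and standard software options, with no new data. Intervals from the imputation analysis become about 6 to 7% wider at ICC .03 with no other follow-up (1.008/.951 = 1.06), about 3% wider where another follow-up is observed for everyone, and less at ICC .01. In simulation at ICC .03 the cluster random intercept brought the ratio of pooled SE to true SD to 1.00–1.01.
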